9.3. Vital Signs

Vital signs will be collected at Screening, Day 1, and Weeks 2, 4, 5, 6, 9, and 12. Moreover, for patients enrolled under version 9 of protocol and later, vital signs are also measured on Day 1 and Day 29 at the start of the visit and at 6 ± 1 , 12 ± 2 , and 24 ± 4 hours after initiation of the trial drug for patients initiating treatment. Those data will be included in descriptive analysis.

Descriptive summaries of observed and change from baseline values will be calculated for systolic blood pressure, diastolic blood pressure, pulse, respiratory rate, and oxygen saturation (SpO_2) by study visit and treatment group within treatment period for patients in Safety Set.

Frequencies and percentages of vital sign interpretation results (normal, abnormal clinically significant, and abnormal not clinically significant) will be summarized by treatment group within treatment period and study visit.

Shifts from baseline for vital sign values normal, abnormal not clinically significant and abnormal clinically significant will be provided for each parameter by treatment group within treatment period and study visit.

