For the remaining efficacy endpoints, continuous and categorical endpoints will be presented using summary statistics or frequencies, respectively; no inference will be performed.

Safety Analyses

Adverse events will be coded using the latest version of the Medical Dictionary for Regulatory Activities (MedDRA). Adverse events that begin after the first dose of dasiglucagon will be defined as treatment-emergent. The overall incidence of AEs will be displayed by system organ class, preferred term, and treatment. The incidence of AEs will also be presented by severity and by relationship to the trial drug. Vital signs, clinical laboratory measures (including hematology, biochemistry, incidence of anti-drug antibodies [ADAs]), electrocardiograms (ECGs), echocardiography, physical examinations, and local tolerability data will be summarized by treatment, where applicable. Out-of-range safety endpoints may be categorized as low or high where applicable.

A SAP will be prepared to provide further details on the methods for statistical analysis, including rules for handling multiplicity and missing data.

SAMPLE SIZE DETERMINATION

Patients will be randomized into the trial if they have at least 3 events of hypoglycemia on average per week, as recorded in the diary during the 2 weeks prior to randomization. It is assumed that patients continuing on standard of care will maintain a similar level through Treatment Period 1, with the number of hypoglycemia events (PG <70 mg/dL or 3.9 mmol/L) during Weeks 2-4, as detected by SMPG following a Poisson distribution

Confidential

	with a mean of 9. The trial is powered to detect a treatment effect of 50%, hence, assuming that the number of hypoglycemia events reported for patients in the dasiglucagon group during Weeks 2-4 will follow a Poisson distribution with a mean of 4.5. At the final analysis, 32 patients will have 99% power testing at a 0.05 significance level. The overall alpha level is strongly controlled in this setting, remaining at or below 0.05.
TRIAL AND TREATMENT DURATION	The overall trial duration is expected to be 15 months. The sequence and maximum duration of the trial periods will be as follows: 1. Screening: at least 14 days up to 28 days 2. Treatment Period 1: 4 weeks 3. Treatment Period 2: 4 weeks 4. Follow-up Period: 4 weeks The maximum trial duration for each patient is approximately 16 weeks. The dasiglucagon treatment duration for each patient is 4 or 8 weeks.

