5.3.6. Anticipated Risks of Dasiglucagon in the Treatment of CHI

In clinical trials with dasiglucagon conducted up to now, the most frequent treatment-related AEs were nausea and vomiting, followed by headache.

Glucagon exerts positive inotropic and chronotropic effects and may, therefore, cause tachycardia and hypertension. Transient increases in heart rate have been observed in clinical trials with dasiglucagon, but not hypertension. On the contrary, several episodes of hypotension have been noted in the clinical program.

Accidental overdose may occur due to inappropriate handling of the infusion pump or due to pump malfunction. Overdose may result in nausea, vomiting, inhibition of GI tract motility, short-term increase in heart rate or blood pressure, and/or hypokalemia. Symptomatic care for nausea and vomiting, as well as monitoring of heart rate, blood pressure, and hypokalemia, is advised.

Injection site reactions are observed with many injectable peptides. In the phase 1 and 2 clinical trials, injection site reactions occurred with a low frequency in all treatment groups (dasiglucagon and marketed glucagons), irrespective of dose.

Overall, the clinical trial data indicate that dasiglucagon has a low risk for induction of ADAs. Out of more than 350 doses of dasiglucagon administered to more than 200 patients, only 1 low-titer transient ADA incident has been reported to date, in a patient after administration of 11 SC doses of dasiglucagon or Lilly Glucagon ranging from 0.03 to 0.6 mg, with low binding and low in vitro neutralizing capability. No apparent clinical effects on PK, PD, or AEs were noted. Due to the crossover trial design, the ADA induction could not be ascribed to a specific treatment. Based on the current clinical experience and the product characteristics, the risk of dasiglucagon inducing an ADA response is considered low.

Administration of glucagon or dasiglucagon may be associated with a risk of allergic reactions similar to those observed for other therapeutic peptides or proteins.

Data on the risks of chronic administration of dasiglucagon are not available. From sporadic reports of extended SC/IV infusion of marketed glucagon and in glucagonoma patients, ¹⁴ sustained exposure to high levels of glucagon may lead to development of skin condition

necrolytic migratory erythema (NME), a highly specific migrating, erythematous rash with predilection for perioral, perianal, and lower leg distribution.¹¹

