12.4.4.3. Vital Signs

Descriptive summaries (mean, SD, median, minimum, and maximum) of actual values and changes from baseline will be calculated for systolic blood pressure, diastolic blood pressure, heart rate, respiratory rate, and SpO₂.

The number of patients with vital signs values categorized as below, within, or above normal ranges will be tabulated showing change from baseline (shift tables) for each parameter.

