9.2. Clinical Laboratory Evaluations

Samples for hematology and chemistry will be collected at the Screening and Weeks 2, 5, 6, 9, and 12. Standard of care blood samples can be used as screening samples if they were collected within 1 week of screening.

Descriptive summaries of observed and changes from baseline values will be presented for clinical laboratory values by study visit and treatment group within treatment period.

Shifts from baseline for clinical laboratory values below, within, or above the normal range will be provided for hematology and chemistry results. Minimum/Maximum post-baseline values will also be included in those shift tables, including values from unscheduled visits.

Frequencies of clinically significant abnormal laboratory values for hematology and chemistry results will be presented by treatment group within treatment period at each study visit.

Laboratory values that are outside the normal range will also be flagged in the data listings, along with corresponding normal ranges. Any out-of-range values that are identified by the investigator as being clinically significant will also be shown in a data listing.

Serum pregnancy test results and antidrug antibodies will be listed.

Immunogenicity data will be analyzed descriptively. No statistical tests are planned. Baseline ADA-positive patients will be calculated as a percentage of the total number of patients whose baseline samples were tested for ADA. Overall ADA incidence, the combined results of treatment induced, and treatment boosted ADA-positive patients, will be calculated as a percentage of the total number of evaluable patients, excluding baseline positive patients without any samples available after drug administration. Titers will be reported as median and interquartile range.

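### SAP 9.3 replaces the protocol's below/within/above vital-sign shift table with one that has no direction, so no SAP table counts children by arm who move low or high without a reported adverse event

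*SAP*

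**What the plan says.** Protocol 12.4.4.3 (version 13.0, all countries except Germany) commits to a directional shift table: "The number of patients with vital signs values categorized as below, within, or above normal ranges will be tabulated showing change from baseline", for each parameter. Section 13.4.4.3 of the German version 14.0 says the same. The safety paragraph of the protocol synopsis is weaker but points the same way: "Out-of-range safety endpoints may be categorized as low or high where applicable".

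SAP 9.3 uses other categories. For frequencies: "Frequencies and percentages of vital sign interpretation results (normal, abnormal clinically significant, and abnormal not clinically significant) will be summarized". For shifts: "Shifts from baseline for vital sign values normal, abnormal not clinically significant and abnormal clinically significant will be provided for each parameter". Neither table distinguishes low from high. SAP 9.3 also keeps numerical summaries: "Descriptive summaries of observed and change from baseline values will be calculated for systolic blood pressure, diastolic blood pressure, pulse, respiratory rate" and oxygen saturation, by visit and treatment group within period.

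For laboratory data, SAP 9.2 keeps direction: "Shifts from baseline for clinical laboratory values below, within, or above the normal range will be provided for hematology and chemistry results". It tabulates clinically significant abnormalities separately.

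The SAP overview names protocol versions 13.0 and 14.0 as its basis, so the difference is between current documents.

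**The concern.** For these parameters the direction of a change is part of the safety question. Protocol 5.3.6 says that glucagon may cause tachycardia and hypertension, and that transient heart-rate increases, but not hypertension, were seen with dasiglucagon. It then adds: "On the contrary, several episodes of hypotension have been noted in the clinical program". Protocol 11.1.8 makes clinically significant blood-pressure or heart-rate changes an adverse event of special interest.

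Under SAP 9.3, a child who moves from normal to low systolic pressure and one who moves from normal to high pressure enter the same cell if both are graded alike. Treatment Period 1 is the only randomized comparison in the trial. If direction is not counted there, a cluster of low or high values that nobody reported as an event would be visible only by reading listings. The two documents would also give different answers to a simple question: how many children in each arm moved out of range, and which way?

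**Working it through.** The plan gives no figure on this point, so there is nothing to reproduce. The check has two parts: which SAP outputs still carry direction, and what a table without direction can and cannot show.

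**1. Outputs for a vital-sign change, by source**

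| Output | Shows direction? | Counts children by arm? | Which changes it covers |
|---|---|---|---|
| Protocol 12.4.4.3 / 13.4.4.3 shift table | Yes | Yes | All recorded values |
| SAP 9.3 shift and frequency tables | No | Yes | All recorded values |
| SAP 9.3 observed and change summaries (n, mean, SD, median, minimum, maximum, per SAP 4.1) | Yes | No | All recorded values |
| SAP 9.4 ECG heart-rate change | Yes | No | Heart rate only |
| SAP 9.1 adverse events by preferred term | Yes, if the term carries it | Yes | Reported events only |
| SAP 9.1.3 events of special interest by preferred term | Yes, if the term carries it | Yes | Reported events of this type only |
| SAP 6.1.8 listings | Yes | No (not tabulated) | All collected data |

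Only the protocol's table has direction, a count by arm, and coverage of values not reported as events. No SAP output has all three.

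**2. Illustration**

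The inputs are up to 32 patients randomized 1:1 (SAP 3.2 and 3.5), hence 32/2 = 16 per arm. The numbers of children who shift are assumed, because the documents give none. All are assumed to start normal and to receive the same significance grade.

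*Opposite directions between arms.* Three dasiglucagon children go low and three SOC children go high.
- SAP table: abnormal 3/16 v 3/16, difference 0.
- Protocol table: low 3/16 v 0/16 = +18.75 points; high 0/16 v 3/16 = −18.75 points.
- Signed change summary: if each shift has size d and the other children do not change, the means are −3d/16 and +3d/16. The difference is −6d/16 = −0.375d, so this summary does reveal the opposite movement.

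With k children shifting in each arm, the SAP difference stays at 0 and the protocol table shows k/16 in each direction: 12.5, 25.0, 37.5 and 50.0 points for k = 2, 4, 6 and 8.

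*Both directions within one arm.* Three children go low and three go high, each by d.
- SAP table: 6/16 = 37.5% abnormal, with no direction.
- Signed change summary: mean (−3d + 3d)/16 = 0; minimum −d; maximum +d. The extremes show that some child moved each way. They do not show how many did, or whether the values lay outside normal for age in a population from 3 months to 12 years.
- Protocol table: 3 low and 3 high.

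The numerical summaries therefore recover a net movement between arms. They do not recover the number of children out of range in each direction.

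**The case against.** The case for leaving SAP 9.3 alone has real force.

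- **Direction survives elsewhere.** A reader might infer that the SAP cannot separate hypotension from hypertension, or that opposite changes between arms would cancel out of sight. The documents do not support either reading. Events coded to those terms are tabulated by preferred term and treatment group within period, hemodynamic changes are also tabulated as events of special interest, and signed changes by arm would diverge. This limits the gap to changes not reported as adverse events.
- **There are two abnormal categories.** Low and high are merged within each, not in a single cell. The zero difference above requires equal grading in the two arms.
- **The protocol's table is not ready to run.** Protocol 10.2.3.1 provides reference ranges for laboratory values, but the documents give none for vital signs. An individual interpretation can allow for age. Protocol 12.4 describes its content as a summary and leaves detail to the SAP. This explains the SAP's choice, and is why ranges must be part of any fix.
- **The assessor is not named.** One might call the SAP categories an unblinded investigator's judgement. SAP 9.3 does not say who interprets the values. The inference rests on the category labels and on SAP 9.4, which names the investigator for ECGs.
- **The change may be declared.** The items visible in SAP Section 10 do not mention it, but that section is incomplete in the text available for review. It cannot be called undeclared.
- **The example is constructed.** This is correct. It shows the mechanism and predicts nothing.

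None of this supplies the missing count. SAP 9.2 shows that the same plan can carry a directional shift table and a clinical-significance table side by side.

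**Conclusion.** The mismatch is plain in the text: the protocol's directional vital-sign shift table is not carried into SAP 9.3, and the replacement merges low and high within each abnormal category. The consequence is limited. No SAP table counts, by arm, the children whose blood pressure, heart rate, respiratory rate or SpO2 moves below or above normal without being reported as an adverse event.

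The size of the loss cannot be estimated from the documents, because no shift rate is given. The 12.5 to 50 point range above rests on assumed counts, 16 per arm and equal grading. The conclusion itself rests only on the wording of the two documents. The issue is confined to descriptive safety reporting and does not touch alpha, power or the primary analysis. It is a cheap improvement worth making, and not a threat to the trial's conclusions.

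**What to change.** In SAP 9.3, restore the protocol's shift table for each vital sign by treatment group within treatment period, using age-appropriate reference ranges written into the SAP before database lock. Keep the interpretation table alongside it, as SAP 9.2 does for laboratory values. If reference ranges are not adopted, split each abnormal category into low and high from the recorded value.

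The cost is choosing the age-band ranges, a short change to the SAP wording and one extra descriptive table. No new data are needed. The choice of ranges involves some judgement, which is why it should be fixed before lock.

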9.4. Electrocardiograms

An ECG will be performed at Screening and Weeks 2, 5, 6, 9, and 12. Moreover, for patients enrolled under version 9 of protocol and later, ECG is also measured at the start of the visit and at 24 ± 4 hours after initiation of trial drug for patients initiating treatment. Those data will be included in descriptive analysis.

Descriptive summaries of observed and change from baseline values will be presented for continuous ECG measures of heart rate, PQ interval, QRS duration, QT interval, and QTcF interval by study visit and treatment group within treatment period.

Frequencies and percentage of patients of investigator interpretation of ECG results (normal, abnormal clinically significant, and abnormal not clinically significant) will be summarized for patients in Safety Set by each treatment group within treatment period and study visit.

Additionally, frequencies and percentage of patients with observed QTcF >450 , >480 , and >500 msec, as well as change from baseline in QTcF >30 , >50 , and >60 msec, will be summarized for patients in the Safety Set by each treatment group within treatment period and study visit.

9.5. Echocardiography

An echocardiogram will be performed at Screening and Weeks 9 and 12.

Frequencies and percentage of echocardiography interpretation results (normal, abnormal clinically significant, and abnormal not clinically significant) will be summarized by patients in Safety Set by study visit, overall.

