Patients' parent(s)/guardian will be trained to perform PG assessments. Events of hypoglycemia will be documented by SMPG measurements. The extent of hypoglycemia (episodes and percent time below the threshold) will be further quantified by CGM measurements during the 2 weeks before randomization (baseline), Weeks 2-4 in Treatment Period 1, and Weeks 6-8 of Treatment Period 2. The CGM results will be masked. During the period where the masked trial CGM is used, patients are not allowed to use another un-masked CGM.

Patients completing the trial will (pending investigator confirmation of continued positive benefit-risk balance) be offered to enter a long-term extension trial (Trial ZP4207-17106) to continue dasiglucagon treatment. Patients who do not continue in the long-term extension trial will have a Follow-up visit performed 4 weeks after stopping dasiglucagon treatment.

[figure not shown]

Figure 1 Trial Design

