8.2.2. Exclusion Criteria

A patient will be excluded from the trial if he or she meets any of the following criteria:

- 1. Previous administration of dasiglucagon (previously referred to as ZP4207).
- 2. Known or suspected allergy to the trial drug or related products.
- 3. Previous participation (randomization) in this trial.
- 4. Circulatory instability requiring supportive medication or presence of pheochromocytoma *United Kingdom*: Presence of hypertension or hypotension, including circulatory instability requiring supportive medication or presence of pheochromocytoma.
- 5. Requires exogenous insulin.
- 6. Body weight of \leq 4 kg (8.8 lbs).
- 7. Documented HbA1c ≥7% subsequent to near-total pancreatectomy and within 6 months prior to screening.
- 8. Known or suspected presence of significant central nervous system disease/injury such that in the investigator's opinion will affect trial participation.
- 9. Use of systemic corticosteroids, e.g., hydrocortisone >20 mg/mg/m² body surface area or equivalent in the 5 days before screening.
- 10. Use of anti-inflammatory biological agents, or other immune-modulating agents in the 3 months prior to screening.
- 11. Aspartate aminotransferase (AST) or alanine aminotransferase (ALT) >2.5 X the upper limit of normal (ULN), or estimated glomerular filtration rate (eGFR) <30 mL/min/1.73m² adjusted by a pediatric formula (e.g., Schwartz formula).
- 12. Any clinically significant abnormality identified on echocardiogram that in the opinion of the investigator would affect the patient's ability to participate in the trial.
- 13. History of laboratory test results obtained before screening that show presence of HIV, hepatitis B surface antigen, hepatitis C antibody, or hepatitis A immunoglobulin M.
- 14. Any recognized clotting or bleeding disorders.
- 15. Has participated in an interventional clinical trial (investigational or marketed product) within 3 months of screening or 5 half-lives of the drug under investigation (whichever comes first), or plans to participate in another clinical trial.
- 16. The use of prescription or non-prescription medications known to cause QT prolongation.

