12.4.4. Safety and Tolerability Analyses

Safety analyses will be conducted using data from the Safety Population (as defined in Section 12.3). Safety assessments will include the evaluation of AEs; clinical laboratory assessments (hematology, biochemistry, and ADAs); vital signs, physical examinations; ECGs, echocardiography, and local tolerability issues. No formal inferential analyses will be conducted for safety variables, unless otherwise noted.

Baseline is defined as the last non-missing assessment before first dose in each treatment period. All safety analyses will be summarized by treatment received within treatment period and by trial visit, if applicable.

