4.1. Introduction

Data processing, tabulation of descriptive statistics, calculation of inferential statistics, and graphical representations will be performed primarily using SAS (release 9.4 or higher). If the use of other software is warranted, the final statistical methodology report will detail what software was used for what purposes.

Continuous (quantitative) variable summaries will include the number of patients (n) with non-missing values, mean, standard deviation (SD), median, minimum, and maximum.

Categorical (qualitative) variable summaries will include the frequency and percentage of patients who are in the particular category or each possible value. In general, the denominator for the percentage calculation will be based upon the total number of patients in the study population for the within each treatment group, unless otherwise specified. The denominator for by-visit displays will be the number of patients in the relevant study population with non-missing data at each visit.

The minimum and maximum will be reported with the same degree of precision (ie, the same number of decimal places) as the observed data. Measures of location (mean and median) will be reported to 1 degree of precision more than the observed data and measures of spread (SD) will be reported to 2 degrees of precision more than the observed data.

Percentages will be presented to 1 decimal place, unless otherwise specified.

Unless otherwise indicated, all testing of statistical significance will be 2-sided with a significance level of $\alpha = 0.05$ (see Section [10 Changes from Planned Analysis](#)).

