11.2. COVID-19 Assessment Analysis

As some patient were still in the study during the COVID-19 pandemic, we have assessed the impact on trial participants as well as the resulting measures taken to address the COVID-19 pandemic.

This assessment was made with blinded data and split in several sections.

- First section was about investigational product and trial withdrawal due to COVID-19. The conclusion was that COVID-19 did not impact the use of investigational drug, and there were no study withdrawals due to COVID-19.
- Secondly we have made an assessment on adverse events. No adverse events were related to COVID-19.
- Then we have made an assessment on Efficacy and Safety:

- Regarding efficacy, we just have one missing fasting tolerance test due to COVID-19. This missing assessment will be handled using the prespecified MI analysis stated in section [8.2](#). No other efficacy endpoint is affected by COVID-19.
Regarding safety, as some visits were done remotely, we have some safety data which are missing for laboratory, vital signs, ECG, Echocardiography, Physical Examination, Local Tolerability. By visit, no more than 10% of subjects had any missing safety assessments. No specific analysis will be done on safety related to COVID-19 as impact is limited.
- As the impact of COVID-19 related to efficacy analysis/endpoints is limited, it has been decided to present a summary table of patients/visits impacted by COVID-19 as well as a listing describing data impacted for each impacted subject
.

12. References

1. US Federal Register. (1998) International Conference on Harmonization; Guidance on Statistical Principles for Clinical Trials. Department of Health and Human Services: Food and Drug Administration [Docket No. 97D-0174]. Federal Register Volume 63, Number 179, pages 49583-49598. September 16, 1998.
2. ASA. (2016) Ethical Guidelines for Statistical Practice. Prepared by the Committee on Professional Ethics, April 2016. <http://www.amstat.org/about/ethicalguidelines.cfm>
3. The Royal Statistical Society: Code of Conduct, 2014.
4. Keene, O.N., J. H. Roger, B. F. Hartley, and M. G. Kenward (2014). “Missing data sensitivity analysis for recurrent event data using controlled imputation.” *Pharmaceut Statist* **13**: 258–264.
5. Little, R. and D. Rubin (1987). Statistical Analysis with Missing Data, New York: Wiley.
6. Carpenter, J. R., and M. G. Kenward (2013). Multiple Imputation and its Application (Statistics in Practice), Wiley.

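### The only planned echocardiography summary (SAP 9.5) gives counts by visit pooled over all patients, so it cannot separate new or worsened findings from persisting ones

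*SAP*

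**What the plan says.** Section numbers for the protocol follow version 13.0; the German version carries the same text under other numbers.

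- **Schedule.** SAP 9.5: "An echocardiogram will be performed at Screening and Weeks 9 and 12". There is none at Week 5, when Treatment Period 1 ends.
- **Summary.** SAP 9.5 plans frequencies and percentages in three categories (normal, abnormal CS, abnormal NCS), which "will be summarized by patients in Safety Set by study visit, overall". It names no shift table and no change from screening. Protocol 12.4.4 lists echocardiography as a safety assessment, but none of its subsections says how to analyse it.
- **Denominator.** SAP 4.1: "The denominator for by-visit displays will be the number of patients in the relevant study population with non-missing data at each visit".
- **Who reaches Week 12.** Protocol 7.1: "Patients who do not continue in the long-term extension trial will have a Follow-up visit performed 4 weeks after stopping dasiglucagon treatment".
- **Who may enter.** Exclusion criterion 12 (Protocol 8.2.2) removes a child with "Any clinically significant abnormality identified on echocardiogram that in the opinion of the investigator would affect the patient's ability to participate in the trial". Other abnormal results are not excluded.
- **Comparable items.** SAP 9.3 gives vital signs a shift table in the same three categories. SAP 9.2 gives laboratory values one against the normal range. SAP 9.4 gives ECG intervals change from baseline.

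**The concern.** Echocardiograms are taken before and after dosing so that a child's later heart examination can be set against the earlier one. The protocol has a reason to look: section 5.3.6 says "Glucagon exerts positive inotropic and chronotropic effects" and adds that there are no data on the risks of chronic dasiglucagon administration.

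The planned table shows the total abnormal at each visit. A total can stay level because the same children remain abnormal, or because some resolve or leave the table while others become abnormal. Those two situations mean different things for safety, and the table cannot tell them apart. At stake is whether the report contains a prespecified count of new or worsened findings, or whether someone has to assemble one afterwards from the listings.

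**Working it through.** The documents give no echocardiogram counts, so there is no figure of the plan's own to reproduce. The counts below are assumptions chosen to show what the table can and cannot say. N = 32 is the planned maximum.

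**1. What the totals allow.** Let *a* children be abnormal at screening and *b* at Week 9, among the same *N* children, with *x* newly abnormal. The persisting number, *b* − *x*, must lie between 0 and *a*, and *x* cannot exceed *N* − *a*. So

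max(0, *b* − *a*) ≤ *x* ≤ min(*b*, *N* − *a*).

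| *a* (screening) | *b* (Week 9) | Table reads | New abnormalities that fit |
|---|---|---|---|
| 3 | 3 | 9.4%, 9.4% | max(0, 0) = 0 to min(3, 29) = 3 |
| 1 | 1 | 3.1%, 3.1% | 0 to 1 |
| 3 | 2 | 9.4%, 6.25% | 0 to 2 |
| 0 | 1 | 0%, 3.1% | exactly 1 |

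In the first row, the upper end means 3 of the 29 children who were normal at screening, or 10.3%. In the third row the percentage falls, yet two new findings remain possible. In the last row nothing is masked.

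**2. The three categories.** For every row to look unchanged, the resolved and the new findings must fall in the same category. A new CS finding against a resolved NCS one raises the CS row by one and lowers the NCS row by one, and so is visible.

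**3. Children missing at Week 9.** On remote visits during the pandemic, SAP 11.2 reports: "By visit, no more than 10% of subjects had any missing safety assessments". Applied to Week 9 echocardiograms as an assumption, 10% of 32 is 3.2, so at most 3 children. Three abnormal at Week 9 then reads 3/29 = 10.3%. If the missing three were those abnormal at screening, all 3 abnormal results at Week 9 are new. If the missing three were normal throughout, possibly none is.

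**4. Week 12.** The number not entering the extension is not given. One abnormal child is 1/2 = 50% of the row if 2 remain, 1/4 = 25% if 4 remain, and 1/8 = 12.5% if 8 remain. The count stands beside the percentage, so the reader sees the small base. The row still describes a selected group and cannot be compared with screening.

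**5. What pooling loses.** By Week 9 one randomized group has had about 8 weeks of dasiglucagon and the other about 4. Pooling removes this exposure split. With 16 per group, one child is 1/16 = 6.25 points.

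**The case against.** The strongest reply is that nothing is lost. SAP 6.1.8 lists all collected data. With at most 32 children and three scheduled echocardiograms each, that is at most 96 results, which a reviewer can read. An untoward new sign meets the adverse event definition in Protocol 11.1.1 and would enter the tables in SAP 9.1. A data monitoring committee and an internal safety committee also review safety during the trial. This largely stands. A reader might infer that a new cardiac abnormality would be hidden from the report, and the documents do not support that. What remains is narrower. Protocol 10.2.3 has explicit rules for recording clinically significant laboratory and ECG findings as adverse events but none for echocardiograms, so only the general definition applies, and a new NCS finding may appear only in the listing.

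Second, the treatment is not unusual within the SAP. Investigator interpretations of ECG (9.4) and physical examination (9.6) get no shift table either. The protocol promises shift tables only for laboratory values and vital signs, and echocardiography is not among the safety endpoints in Protocol 6.2.5. This stands: the SAP does not depart from its protocol.

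Third, the risk passage goes on to name tachycardia and hypertension, which vital signs and ECG follow directly. It does not name an echocardiographic abnormality as the expected harm. This also stands, and it lowers the weight of the point.

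Fourth, a reader might infer that pooling discards a treated-versus-control comparison, or breaches Protocol 12.4.4: "All safety analyses will be summarized by treatment received within treatment period and by trial visit, if applicable". Neither follows. No echocardiogram is scheduled at the end of Period 1, and every patient is planned to receive dasiglucagon in Period 2. Week 9 therefore has no group on standard of care alone, and the rule applies only where applicable.

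**Conclusion.** The point holds as a limitation of the planned summary. SAP 9.5 cannot give the number of children with a new or worsened echocardiogram whenever some child is abnormal at screening and findings resolve, or children leave the table, between visits. With the assumed 3 of 32 at both visits, the uncertainty is 0 to 3 children. It shrinks to nothing if every screening echocardiogram is normal. The Week 12 row adds little to a comparison with screening because it holds a selected subset of unknown size.

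The point does not show that data go uncollected, that clinically significant findings would be missed, or that a controlled comparison was available and dropped. No efficacy inference is affected. It is a modest improvement to a descriptive safety table, worth making because it is cheap and because the SAP already uses the format for vital signs.

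**What to change.** Add to SAP 9.5 a shift table on paired results, from screening to Week 9 and from screening to the last post-dose echocardiogram. Use the three existing categories plus missing, and state the number of children with a new or worsened finding. The screening result serves as baseline in both groups because it precedes dosing.

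Present the table overall and, descriptively, by randomized sequence (about 8 versus about 4 weeks of dasiglucagon by Week 9), with a note that Week 9 has no group on standard of care alone. The by-visit summary can stay beside it.

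The cost is a few lines of SAP text and one extra descriptive table with small cells, in the format of SAP 9.3. It needs no new assessments and no change to patient management.
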